11.3. Adverse Event and Device Deficiency Reporting Requirements

Adverse events and device deficiencies should be reported by the investigator to Medtronic as soon as possible after the event occurs, but no later than the timeframes listed in Table 7 or local requirements, whichever is more stringent.

In addition, investigators are obligated to report adverse events and device deficiencies in accordance with the requirements of their reviewing EC/IRB and local regulations.

Table 7 Adverse Event and Device Deficiencies Reporting Requirements by Investigator

Event Type to report	Timeframe for Reporting to Medtronic	Reporting To Regulatory Authority and Ethics Committee

• Serious Adverse Device Effect (SADE)• Unanticipated Serious Adverse Device Effect (USADE)• Serious Adverse Event (SAE)• Adverse Device Effect (ADE)• Device Deficiency that might have led to a SADE• 	Report immediately, but no later than 72 hours after investigational site study personnel's awareness of the event (or sooner if required by local regulation)	All countries: Submit per local reporting requirements

• Adverse Event (AE)• Device Deficiency (DD)	Report in a timely manner from the investigator's / site's first knowledge of the event	All countries: Submit per local reporting requirements

Medtronic is obligated to report adverse events and device deficiencies that occur during this study to the regulatory authorities and EC/IRB as per local requirements. For Germany, refer to German Local Amendment A, or subsequent versions, for more details.

Table 8 Adverse Event and Device Deficiencies Reporting Requirements by Medtronic to Regulatory Authorities & EC

Event Type to report	To Regulatory Authorities	To Ethics Committees

• Serious Adverse Device Effect (SADE)• Unanticipated Serious Adverse Device Effect (USADE)• Serious Adverse Event (SAE)• Device Deficiency that might have led to a SADE• Adverse Event (AE)• Adverse Device Effect (ADE)• Device Deficiency (DD)	
All countries: Submit per local reporting requirements Reporting timeframe as per local requirement
 
For Germany, refer to German Local Amendment A, or subsequent versions, for more details.
	
All countries: Submit per local reporting requirements

In addition, Medtronic shall prepare and submit complete, accurate, and timely study reports, as per local reporting requirements.

11.3.1. Reporting of Adverse Events

The investigator or designee will record all AEs while the subject is enrolled in the clinical study (including at minimum the following information: date of the adverse event, date of first awareness by investigator, action taken, outcome status and resolution, and assessment of both the seriousness and the relationship to the investigational device and procedure).

Each AE needs to be assessed for its device or procedure relatedness. A device related AE is associated with the use of the study device (e.g. infection of sensor site or infusion set occlusion resulting in DKA). A procedure related AE is associated with testing related to the study procedures specified in the CIP.

Examples of device or procedure related AEs include:

- **Device** related: insertion site infection
- Serious adverse **device effect**: cellulitis at device insertion site requiring hospitalization
- **Procedure** related AE: bruising at IV insertion site

Adverse events that have not resolved at the time of the subject's discontinuation or completion of the study should have an "outcome" of Not Recovered/Not Resolved at study end in subject source and on an eCRF. The investigator should ensure that subject is aware of any follow-up or additional treatment that is required for any ongoing AE at end of study participation; however, there will be no eCRF entry for the ongoing follow-up.

Subjects participating in the study have diabetes and are expected to experience hypoglycemia and/or hyperglycemia. These normal events are not expected to be reported to sponsor on an AE eCRF as this is not considered an untoward event, but rather an expected occurrence. Any glycemic excursion that meets the protocol definition of Severe Hypoglycemia, Severe Hyperglycemia or DKA is considered an untoward event and a worsening from the subject's baseline and would be reported to sponsor on an AE eCRF.

Medical conditions should only be reported to sponsor on an AE eCRF, if there is a worsening from the subject's baseline. For example, a subject previously diagnosed with Asthma is hospitalized for severe asthma attack would be a reportable event.

Adverse events will be documented in the subject source file and reported to sponsor on an eCRF. The investigational center is responsible for documentation of AEs including obtaining source documents related to the event, such as emergency medical technician/paramedic reports, hospital records (admission summary; lab results, test results, discharge summary) or device uploads to support the event. Source documents will be reviewed to determine if additional AEs have occurred and require reporting.

The Adverse Event (AE) information will be collected throughout the study and reported to Medtronic on an Adverse Event eCRF. One Adverse Event eCRF will be completed for *each adverse event*, including AEs that require immediate reporting. The Adverse Event eCRF must be validated and saved "complete", for submission to Medtronic. See the Adverse Event eCRF for the information to be reported for each Adverse Event.

In case the database is not functioning, the site staff will report any safety data (AE/DD) on the applicable CRF via email to [contact] as soon as possible and/or within reporting guidelines outlined in this document (see Table 7 Adverse Event and Device Deficiencies Reporting Requirements by Investigator). In the event the internet is not functioning, the site will inform the Medtronic Study Manager via phone (see Sponsor list for contact details).

In case the Adverse Event is related to a non-Medtronic market released device (i.e. study meter) used during the study, post market surveillance applies, and the investigator is responsible for immediate reporting of the product complaint via the regular channels for market released products.

In case the investigator requires information from the sponsor in an emergency situation, the investigator can contact their local clinical referent or the Study Manager. Contact details of the Study Manager are given in the Sponsor List.

11.3.2. Reporting of Device Deficiencies

Device Deficiency information will be collected throughout the study and reported to Medtronic, via the electronic CRF. Vigilance reporting will be done for CE-Marked devices, according to these CRF reported data.

All Device Deficiencies that did not lead to an Adverse Event should be reported on the Device Deficiency eCRF, one for each Device Deficiency, completing as much information as is available. This Device Deficiency eCRF must be validated / saved “complete” for submission to Medtronic.

See the Device Deficiency eCRF for the information to be reported for each Device Deficiency that did not lead to an Adverse Event.

Device deficiencies that did not lead to an Adverse Event, but could have led to a SADE:

- a) if either suitable action had not been taken,
- b) if intervention had not been made, or
- c) if circumstances had been less fortunate

also defined as Device Deficiencies with SADE potential require immediate reporting to the sponsor via completion of the applicable CRF, to IRB/EC and to regulatory authority per local reporting requirements ISO14155:2020 (Refer to Table 8). For Germany, refer to German Local Amendment A, or subsequent versions, for more details.

All Device deficiencies will be reported to Investigators, Regulatory Authorities and IRB/IEC as part of the Study report(s).

In case technical issue occurs with the electronic CRF (i.e. Internet access, system maintenance...), initial reporting for Device Deficiencies that require immediate reporting (see Table 7), may be done via email: [contact]. In the event the internet is not functioning, the site will inform Medtronic Study Manager via phone (see Sponsor list for contact details).

The site should contact their local clinical referent or the study manager in case of questions. Contact details are given in the Sponsor List.

11.4. Adverse Event and Device Deficiency review process

The potential adverse events (risks) and their mitigations associated with the use of these devices are identified in the Instructions for Use (IFU) for the CE-marked commercially available devices/consumables and in the Investigator Brochure (IB) for the pre-market devices/consumables (also see Section 10.1 of this CIP).

All Adverse Events and Device Deficiencies will be reviewed by Medtronic. This review will include the determination whether the Adverse Event/Device Deficiency meets regulatory reporting requirements. The sponsor will ensure timely Adverse Event/Device Deficiency reporting to meet global regulatory requirements.

Medtronic will immediately report any Adverse Events/Device Deficiencies that are associated with the commercially released devices to the Medtronic Diabetes Complaint Handling Unit. The Diabetes Complaint Handling Unit will ensure prompt review, and appropriate reporting.

11.5. Causality Assessment

An AE is not automatically related to the study device or procedure simply because the subject is wearing the device and participating in the study. The event should be reviewed to determine if the device or study procedure could have possibly caused the event and therefore is related to the study device or procedure.

Causality assessment is the determination of the relationship between an AE and the device being studied. It is expected that the investigational center will review all elements surrounding the AE to properly assess the causality of the event to the study device or to a study procedure.

Investigators should classify the relationship between the AE and the study device or study procedures using one of the five possible causality categories listed below:

1) Not related: relationship to the device or procedures can be excluded when:

- The event is not a known¹ side effect of the product category the device belongs to or of similar devices and procedures;
- The event has no temporal relationship with the use of the investigational device or the procedures
- The event does not follow a known response pattern to the medical device (if the response pattern is previously known) and is biologically implausible;
- The discontinuation of medical device application or the reduction of the level of activation/exposure - when clinically feasible - and reintroduction of its use (or increase of the level of activation/exposure), do not impact on the event;
- The event involves a body-site, or an organ not expected to be affected by the device or procedure;
- The event can be attributed to another cause (e.g. an underlying or concurrent illness/ clinical condition, an effect of another device, drug, treatment or other risk factors);
- The event does not depend on a false result given by the investigational device used for diagnosis², when applicable;
- Harms to the subject are not clearly due to use error;
- In order to establish the non-relatedness, not all the criteria listed above might be met at the same time, depending on the type of device/procedures and the event.

¹ When the event is not a known side effect of the product category the device belongs to or of similar devices and procedures, generally is considered "not related". Yet, the unexpected effect shall not be excluded from evaluation and reporting.

² If an investigational device gives an incorrect diagnosis, the patient might, for example, receive an unnecessary treatment and incur all the risks that accompany that treatment, or might be incorrectly diagnosed with a serious disease. In other cases, the patient might not receive an effective treatment (thereby missing out on the benefits that treatment would confer) or might not be diagnosed with the correct disease or condition.

2) Unlikely: the relationship with the use of the device seems not relevant and/or the event can be reasonably explained by another cause, but additional information may be obtained.

3) Possible: the relationship with the use of the investigational device is weak but cannot be ruled out completely. Alternative causes are also possible (e.g. an underlying or concurrent illness/ clinical condition or/and an effect of another device, drug or treatment). Cases where relatedness cannot be assessed or no information has been obtained should also be classified as possible.

4) Probable: the relationship with the use of the investigational device seems relevant and/or the event cannot reasonably be explained by another cause, but additional information may be obtained.

5) Causal relationship: the event is associated with the investigational device or with procedures beyond reasonable doubt when:

- The event is a known side effect of the product category the device belongs to or of similar devices and procedures;
- The event has a temporal relationship with investigational device use/application or procedures;
- The event involves a body-site or organ that:
 - o The investigational device or procedures are applied to;
 - o The investigational device or procedures have an effect on;
- The event follows a known response pattern to the medical device (if the response pattern is previously known);
- The discontinuation of medical device application (or reduction of the level of activation/exposure) and reintroduction of its use (or increase of the level of activation/exposure), impact on the event (when clinically feasible);
- other possible causes (e.g. an underlying or concurrent illness/ clinical condition or/and an effect of another device, drug or treatment) have been adequately ruled out;
- Harm to the subject is due to error in use;
- The event depends on a false result given by the investigational device used for diagnosis, when applicable;
- In order to establish the relatedness, not all the criteria listed above might be met at the same time, depending on the type of device/procedures and the event.

Example: A severe hyperglycemia AE with the following event description would have the following causality assessment for device relatedness:

Improved glucose without an infusion set/site change	Not related
Changed infusion set with glucose improvement	Possible
Infusion set fell out, bent cannula, occlusion alarm	Causal relationship

12. Data Review Committees

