5.3.2.1. Safety Endpoint

- Number of severe hypoglycemic events
- Number of DKA events
- Number of Serious Adverse Events (SAE)
- Number of Serious Adverse Device Effects (SADE)
- Number of Unanticipated Serious Adverse Device Effects (USADE)
- Number of Device deficiencies

The above endpoints will also be assessed in Cohort B in an exploratory manner, as well as the difference in the mean HbA1c change (6 months - baseline) between the AHCL and the MDI + RT-CGM arms.

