7.12. Comparator

Subject enrolled in the study are treated with any Multiple Daily Injection device and Flash or Continuous Glucose Monitoring systems. Subject can use any model, as prescribed per standard of care prior to screening, through the commercial pathway. There is no device accountability requirement for the comparator for the purpose of this study. Subjects will continue to use it as needed throughout the study, as per randomization assignment.

Examples of Flash Glucose Monitoring Systems: Abbott Freestyle Libre 1 or 2.

Examples of Continuous Glucose Monitoring systems: Dexcom G4, G5, G6; Medtronic Guardian Connect; Sugarbeat.

Any other model that may be/become available for prescription during the study can also be used.

8. Selection of Subjects

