11.2. Definitions and Classification

Medtronic uses the definitions provided in ISO 14155:2020 for AE definitions.

Where the definition indicates "device", it refers to any device used in the study. This might be the device under investigation, or any market released component of the system. Medtronic follows MEDDEV 2.7/3 revision 3 (or subsequent versions) guidelines for classifying causality levels; but will apply these causality definitions across all events, not only serious adverse events and definitions have been adapted accordingly.

Severe Hypoglycemia is an event requiring assistance of another person due to altered consciousness to actively administer carbohydrate, glucagon, or other resuscitative actions. This means that the subject was impaired cognitively to the point that he/she was unable to treat his or her self, was unable to verbalize his or her needs, and was incoherent, disoriented and/or combative.

These episodes may be associated with sufficient neuroglycopenia to induce seizure or coma. Plasma glucose measurements may not be available during such an event, but neurological recovery attributable to the restoration of plasma glucose to normal is considered sufficient evidence that the event was induced by a low plasma glucose concentration. (*Adapted from American Diabetes Association Workgroup on Hypoglycemia, Diabetes Care 28:1245-1249, 2005*)

Severe Hyperglycemia is defined as hyperglycemia (blood glucose greater than >300 mg/dL (16.7 mmol/L) with blood glucose ketones greater than > 0.6 mmol/L or accompanied by symptoms of nausea, vomiting or abdominal pain.

Diabetic Ketoacidosis/DKA diagnostic criteria: blood glucose greater than > 250 mg/dL (or greater than > 13.9 mmol/L), arterial pH less than < 7.3 , bicarbonate less than < 15 mEq/L, moderate ketonuria or ketonemia and requiring treatment within a health care facility. (*American Diabetes Association-Diabetes Care, Volume 27, Supplement 1, January 2004; S94-S102*)

Hyperglycemic events will be recorded as DKA if the event includes the presence of all of the following:

- Arterial blood pH less than < 7.30 or serum bicarbonate less than < 15 mEq/L
- Blood glucose greater than > 250 mg/dL (or greater than > 13.9 mmol/L)
- Serum ketones or large/moderate urine ketones
- Symptoms such as polyuria, polydipsia, nausea, or vomiting
- Treatment provided in a health care facility

Adverse Event (AE): (ISO 14155:2020, 3.2)

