Any untoward medical occurrence, unintended disease or injury, or untoward clinical signs (including abnormal laboratory findings) in subjects, users or other persons, whether or not related to the investigational medical device and whether anticipated or unanticipated.

NOTE 1: This definition includes events related to the investigational medical device or the comparator.

NOTE 2: This definition includes events related to the procedures involved.

NOTE 3: For users or other persons, this definition is restricted to events related to investigational medical devices or comparators.

Adverse Device Effect (ADE): (ISO 14155:2020, 3.1)

Adverse event related to the use of an investigational medical device

NOTE 1: This definition includes AEs resulting from insufficient or inadequate instructions for use, deployment, implantation, installation, or operation, or any malfunction of the investigational medical device.

NOTE 2: This definition includes any event resulting from an error use or from intentional misuse of the investigational medical device.

NOTE 3: this includes 'comparator' if the comparator is a medical device.

Serious Adverse Event (SAE): (ISO 14155:2020, 3.45)

Adverse event that led to any of the following

- a) death,
- b) serious deterioration in the health of the subject, users or other persons as defined by one or more of the following:
 - 1) a life-threatening illness or injury, or
 - 2) a permanent impairment of a body structure or a body function, including chronic disease, or
 - 3) in-patient or prolonged hospitalization, or
 - 4) medical or surgical intervention to prevent life-threatening illness or injury or permanent impairment to a body structure or a body function,
- c) fetal distress, fetal death or a congenital abnormality or birth defect including physical or mental impairment

NOTE 1: Planned hospitalization for a pre-existing condition, or a procedure required by the CIP, without serious deterioration in health, is not considered a *serious adverse event*.

For the purpose of this study, the term "life-threatening" in the definition of "serious" refers to an event in which the patient was at risk of death at the time of the event; it does not refer to an event which hypothetically might have caused death if it were more severe. (ICH Topic E 2 A Clinical Safety Data Management: Definitions & Standards for Expedited Reporting. EMEA 2006)

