Definition for Germany only: **Serious Adverse Event (SAE):** (*MPSV § 2 Definition Abs 5*)

A serious adverse event is an event that occurs in a clinical investigation subject to approval or occurring in a performance evaluation which led, might have led or could lead directly or indirectly to death or serious deterioration of health of the subject, the user or a third party, without consideration if the event has been caused by the medical device itself; this applies accordingly to serious adverse events occurring in a clinical investigation or performance evaluation for which an exemption of the approval authorization as per MPG § 20 paragraph 1 sentence 2 has been granted.

Serious Adverse Device Effect (SADE): (*ISO 14155:2020, 3.44*)

Adverse device effect that has resulted in any of the consequences characteristic of a serious adverse event.

Unanticipated Serious Adverse Device Effect (USADE): (*ISO 14155:2020, 3.51*)

Serious adverse device effect which by its nature, incidence, severity or outcome has not been identified in the current risk assessment

NOTE 1: ASADE is an effect which by its nature, incidence, severity or outcome has been identified in the risk assessment.

Serious Health Threat (*ISO 14155:2020, 3.46*)

Signal from any adverse event or device deficiency that indicates an imminent risk of death or a serious deterioration in the health in subjects, users or other persons, and that requires prompt remedial action for other subjects, users or other persons

NOTE 1: This would include events that are of significant and unexpected nature such that they become alarming as a potential serious health hazard or possibility of multiple deaths occurring at short intervals.

Device deficiency: (*ISO 14155:2020, 3.19*)

Inadequacy of a medical device with respect to its identity, quality, durability, reliability, usability, safety or performance.

NOTE 1: DD include malfunctions, use errors and inadequacy in the information supplied by the manufacturer including labeling.

NOTE2: This definition includes device deficiencies related to the investigational medical device or the comparator.

Relatedness:

Device Related: An AE that results from the presence or performance (intended or otherwise) of the device.

Procedure Related: An AE that occurs due to any study procedure (ie. Blood draw).

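### SADE and USADE are defined to include comparator devices, but the causality rules give comparator-related events no explicit route into those counts

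*Protocol*

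**What the plan says.** **Definitions.** In Protocol 11.2 the adverse device effect (ADE) entry carries the extension "NOTE 3: this includes 'comparator' if the comparator is a medical device". A SADE is then an "Adverse device effect that has resulted in any of the consequences characteristic of a serious adverse event", and a USADE is a SADE not identified in the risk assessment, so both inherit the extension. Section 7.12 describes the comparator: "Subject enrolled in the study are treated with any Multiple Daily Injection device and Flash or Continuous Glucose Monitoring systems". On the word *device* in its definitions, 11.2 says "it refers to any device used in the study. This might be the device under investigation, or any market released component of the system".

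**Recording and rating.** Section 11.3.1 lists the minimum adverse event record, including "assessment of both the seriousness and the relationship to the investigational device and procedure". Section 11.5 states: "Investigators should classify the relationship between the AE and the study device or study procedures", using five categories. In 12.1 the CEC uses three categories for device and procedure relatedness.

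**Use.** SADE and USADE counts are safety endpoints in 5.3.2.1. SAP 7.10.3 reports them by study arm. SAP 7.1.3.3 provides for comparing safety between the study period and the continuation phase.

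**The concern.** The definition and the measurement cover different sets of devices. By definition, a serious event caused by a wrong FGM reading or a faulty injection device in a control subject is a SADE. Under the rating instructions, the investigator is asked about the study or investigational device and about procedures, and is not asked about the FGM or the injection device.

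At stake is how the SADE and USADE rows are read. The same kind of event, such as a serious hypoglycaemic episode after a false sensor reading, can count as a SADE on AHCL but has no clear path to one on MDI + FGM. Within the control group, the switch to AHCL at Visit 9 also changes which of a subject's therapy devices can be rated. SADE counts could therefore rise between periods with no change in underlying risk.

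**Working it through.** There is no planned figure to reproduce: neither document gives a rate, expected count, margin or hypothesis for SADE or USADE. The check compares the texts, followed by one illustration of exposure.

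**Step 1: is the comparator inside the definition?** Yes. ADE NOTE 3 includes a comparator that is a medical device; 7.12 names injection devices and FGM/CGM; SADE builds on ADE and USADE on SADE.

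**Step 2: is the comparator inside the rating?**

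| Place | Target of the rating | Comparator named? |
|---|---|---|
| 11.3.1, minimum AE record | Investigational device and procedure | No |
| 11.5, statement of purpose | The device being studied | No |
| 11.5, *Unlikely* | The device, unqualified | No |
| 11.5, *Possible*, *Probable* | Investigational device | No |
| 11.5, *Causal relationship* | Investigational device or procedures | No |
| 11.5, worked example | Infusion-set problems | No |
| 12.1, CEC | Device and procedure | No |

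**Step 3: where does a comparator-caused event go?** Among the criteria for *Not related*, 11.5 lists attribution to another cause and gives another device's effect as an example. An event clearly traced to the FGM meets that criterion. Section 11.3.1 also sends complaints about events related to non-Medtronic marketed devices used in the study to the usual product channels, and adds no relatedness rating for them.

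**Step 4: which endpoints depend on this?** Of the endpoints in 5.3.2.1, only SADE and USADE pass through the causality rating. Severe hypoglycaemia, DKA and SAE are defined without reference to cause. Device deficiencies have their own definition in 11.2, repeated in SAP 7.10.3, which already covers the comparator.

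**Step 5: could the size be read off the counts?** No. For illustration only, take Cohort A with 70 randomised 1:1, so 35 controls over 0.5 years: 35 × 0.5 = 17.5 patient-years. With an assumed true rate r of comparator-related serious effects, the expected count is 17.5 × r and the Poisson probability of seeing none is exp(−17.5 × r).

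| Assumed rate per 100 patient-years | Expected count | Probability of zero |
|---|---|---|
| 1 | 0.18 | 0.84 |
| 2 | 0.35 | 0.70 |
| 5 | 0.88 | 0.42 |
| 10 | 1.75 | 0.17 |

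At the lower assumed rates a zero is likely even with full comparator rating. A low control count would therefore not reveal whether the rule or the small exposure produced it.

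**The case against.** The best defence is that the text is ambiguous and does not exclude the comparator. Section 11.2 opens by taking *device* to mean any device used in the study, and its short definition of device-related refers simply to the device. *Study device* is never defined as leaving the comparator out. Unassessable cases default to *Possible*. The AE record in 11.3.1 is a minimum, and the case report form is held under separate cover (17.4), so it may already have a comparator field.

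Part of this stands. The form cannot be seen, and a site could read the rules broadly. But the opening of 11.2 governs its definitions, and its examples are the investigational device and components of the system. Read broadly, it widens the gap with 11.5. The *Possible* default is for events that cannot be assessed; an event traced to an FGM reading can be assessed, and 11.5 points it towards *Not related*.

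The objection that the impact is limited also stands. Protocol 13.6 treats safety tests as exploratory with no significance claimed, SAP section 4 calls all its analyses exploratory, and no decision rule uses SADE or USADE.

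A reader might infer that control-arm SADE and USADE counts are close to zero by construction. The documents do not support that: controls wear the blinded sensor and transmitter, use the study meter and undergo study procedures, all of which can yield ratable effects.

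A reader might also try to size the gap from blinded-sensor wear: 2 × 14 = 28 days out of about 204 between Visits 4 and 9, or 14%. That share is not a measure of the gap. Blinded readings are unavailable to subjects and staff (7.4) and cannot cause an event through a treatment decision.

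**Conclusion.** The mismatch is real and should be corrected. Following 11.3.1 and 11.5 as written would leave serious events related to the injection device, FGM or CGM out of SADE and USADE counts whose definition includes them. On those two endpoints the comparator side can only be undercounted, so a contrast between arms, or between the MDI and AHCL periods in controls, would tend to run against AHCL. How much cannot be derived from the documents.

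A reader might go further and conclude that the trial's safety conclusion is biased against AHCL. That does not follow. The affected counts are descriptive, and a severe hypoglycaemic episode, DKA event or other SAE is counted in both arms whatever its cause. Device deficiencies are likewise unaffected.

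The conclusion assumes that sites and the CEC apply 11.5 as worded and that the unseen case report form adds no comparator rating.

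**What to change.** Define *study device* in 11.2. In 11.3.1, 11.5 and 12.1, add the comparator device (injection device, FGM/CGM) as a separate rated target with the same categories, for investigators and the CEC alike, so that SADE and USADE follow NOTE 3 in both arms. The cost is slightly more assessment work for control-arm events and possibly one case report form field.

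If that is no longer possible, reconcile NOTE 3 with the rating rules. State in Protocol 5.3.2.1 and SAP 7.10.3 that SADE and USADE cover sponsor-supplied devices and study procedures only, and that they are not to be compared between arms or between MDI and AHCL periods. Leave the device-deficiency endpoint as it is. This fallback costs wording only, but gives up any count of comparator-related serious device effects.
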